5.3 General Concomitant Medication and Supportive Care Guidelines

Concomitant medication is defined as any prescription or over-the-counter preparation including vitamins and supplements. All required and optional/allowed concomitant medications must be recorded from screening through the end of the participant's study participation. Any change in concomitant medications must be recorded.

5.3.1 Required Concomitant Medications

CONFIDENTIAL

This document is confidential. Do not disclose or use except as authorized.

Female participants of childbearing potential must agree to use methods of contraception for the duration of the study. Male participants must agree to use a barrier method of contraception for the duration of the study if sexually active with a female of childbearing potential. Surgically sterilized patients are except from contraception requirements.

All participants will receive 400 mg orally twice daily of acyclovir or valacyclovir 1000 mg orally daily, unless contraindicated, for Herpes zoster prophylaxis for the duration of the trial and for at least 6 months following completion of ixazomib treatment.

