lymphomas (Cartron 2002; Weng 2003), and has lead to U.S. FDA clearance for such testing. The impact of FcγRIIIA-158 polymorphisms in predicting categorical response attainment in WM patients has recently been reported. Hunter et al demonstrated that better categorical responses (i.e. VGPR or better) were associated with V/V or V/F at FcγRIIIA-158 in patients who received combination therapy with rituximab (Treon 2011). As such, as part of these studies we will seek to determine the impact of FcγRIIIA-158 polymorphisms on categorical response attainment in WM patients in this study.

3.PARTICIPANT SELECTION

3.1Eligibility Criteria

Participants must meet the following criteria on screening examination to be eligible to participate in the study:

Each patient must meet all of the following inclusion criteria to be enrolled in the study:

1. Male or female patients 18 years or older.
2. Voluntary written consent must be given before performance of any study related procedure not part of standard medical care, with the understanding that the patient may withdraw consent at any time without prejudice to future medical care.
3. Female patients who:
 - Are postmenopausal for at least 1 year before the screening visit, OR
 - Are surgically sterile, OR
 - Are of childbearing potential,
 - agree to practice 2 effective methods of contraception, at the same time, from the time of signing the informed consent form through 90 days after the last dose of study drug, OR
 - Agree to practice true abstinence when this is in line with the preferred and usual lifestyle of the subject. (Periodic abstinence [eg, calendar, ovulation, symptothermal, post-ovulation methods] and withdrawal are not acceptable methods of contraception.)

Male patients, even if surgically sterilized (ie, status post-vasectomy), must agree to one of the following:

- Agree to practice effective barrier contraception during the entire study treatment period and through *90 days* after the last dose of study drug, OR
 - Agree to practice true abstinence when this is in line with the preferred and usual lifestyle of the subject. (Periodic abstinence (eg, calendar, ovulation, symptothermal, post-ovulation methods] and withdrawal are not acceptable methods of contraception.)

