6.1.4 Precautions and Restrictions

- **Fluid deficit should be corrected before initiation of treatment and during treatment.**
- **Nonsteroidal anti-inflammatory drugs (NSAIDs) should be avoided with impaired renal function given reported NSAID-induced renal failure in patients with decreased renal function.**

Pregnancy

It is not known what effects ixazomib has on human pregnancy or development of the embryo or fetus. Therefore, female patients participating in this study should avoid becoming pregnant, and male patients should avoid impregnating a female partner.

CONFIDENTIAL

This document is confidential. Do not disclose or use except as authorized.

Nonsterilized female patients of reproductive age group and male patients should use effective methods of contraception through defined periods during and after study treatment as specified below.

Female patients must meet 1 of the following:

- **Postmenopausal for at least 1 year before the screening visit, or**
- **Surgically sterile, or**
- **If they are of childbearing potential, agree to practice 2 effective methods of contraception from the time of signing of the informed consent form through 90 days after the last dose of study drug, or**
- **Agree to practice true abstinence, when this is in line with the preferred and usual lifestyle of the subject. (Periodic abstinence [eg, calendar, ovulation, symptothermal, postovulation methods] and withdrawal are not acceptable methods of contraception.)**

Male patients, even if surgically sterilized (ie, status postvasectomy) must agree to 1 of the following:

- **Practice effective barrier contraception during the entire study treatment period and through 90 days after the last dose of study drug, or**
- **Agree to practice true abstinence, when this is in line with the preferred and usual lifestyle of the subject. (Periodic abstinence [eg, calendar, ovulation, symptothermal, postovulation methods for the female partner] and withdrawal are not acceptable methods of contraception.)**

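### Section 5.3.1 exempts all surgically sterilised patients from contraception, while 3.1 and 6.1.4 bind men even if surgically sterilised

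*Combined protocol and SAP*

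**What the plan says.** Three current sections set contraception rules.

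- **Section 3.1, inclusion criterion 3.** A woman qualifies by being postmenopausal or by surgical sterility ("Are surgically sterile, OR"). If she could conceive, she must "agree to practice 2 effective methods of contraception, at the same time" until 90 days after the last dose, or practise true abstinence. For men the criterion reads "Male patients, even if surgically sterilized (ie, status post-vasectomy), must agree to one of the following", and the options are barrier contraception to the same 90-day point or true abstinence.
- **Section 6.1.4, Precautions and Restrictions.** The scheme is repeated. Surgical sterility ("Surgically sterile, or") is an option on the female list only. The male list opens with "Male patients, even if surgically sterilized (ie, status postvasectomy) must agree to 1 of the following", and its first option is "Practice effective barrier contraception during the entire study treatment period and through 90 days after the last dose of study drug". The stated reason is that "It is not known what effects ixazomib has on human pregnancy or development of the embryo or fetus".
- **Section 5.3.1, Required Concomitant Medications.** Women of childbearing potential are to use contraception, with no number of methods stated. Men are to use a barrier method if they have sexual relations with a woman who could conceive. Both duties run for the length of the study. The paragraph then closes with "Surgically sterilized patients are except from contraception requirements".

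**The concern.** The closing sentence of 5.3.1 has no limit by sex, so it releases a vasectomised man from a duty that two other sections place on him by name. No clause says which section prevails. Section 5.3.1 belongs to the treatment plan, where staff may well look once a participant is on therapy. A site that followed it as written would drop a safety rule that the protocol states twice. What is at stake is consistent protection against partner pregnancy. The protocol treats that as a safety matter: section 11.2 requires immediate reporting if a male participant's partner becomes pregnant.

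**Working it through.** No plan figure depends on this point, so the check is a comparison of texts.

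**Step 1. Compare the rules by group.**

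| Group | 3.1 criterion 3 and 6.1.4 | 5.3.1 | Result |
|---|---|---|---|
| Surgically sterile women | No contraception required | Exempt | Agree |
| Women of childbearing potential | Two effective methods to 90 days after last dose, or true abstinence | Contraception, number of methods not stated, while the study lasts | 5.3.1 looser |
| Men not sterilised | Barrier to 90 days after last dose, or true abstinence, whatever the partner's status | Barrier while the study lasts, only if the partner could conceive | 5.3.1 looser |
| Surgically sterilised men | Same duty as other men, stated expressly | Exempt, stated expressly | Contradiction |

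Only the last row sets an express duty against an express release. In the two looser rows 5.3.1 is less demanding or silent, and a site can satisfy every section by following the stricter one.

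**Step 2. Can the exemption be read as covering women only?** It speaks of patients and directly follows the sentence on men. The female rule in 5.3.1 already reaches only women of childbearing potential, so sterile women were outside it before the exemption was added. Confined to women, the sentence would do nothing. The group whose position it changes is sterilised men. Section 6.1.4 points the other way: its introductory sentence lets sterilisation narrow the rule for women and leaves men unqualified.

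**Step 3. How much does the period wording matter?** This bears on the third looser point, not on the contradiction. The shortfall against the 90-day rule is max(0, 90 − E), where E is the number of days from last dose to the end of the study. The protocol does not define that end for this purpose, so E is an assumption:

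- Study ends on the day of the last dose: 90 − 0 = 90 days.
- Study ends at the off-treatment visit (section 9: 4 weeks ± 2 weeks after completing treatment, counted here from the last dose): 90 − 28 = 62 days, with a range from 90 − 42 = 48 to 90 − 14 = 76.
- Two-year follow-up counts as study (about 730 days): no shortfall.

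Section 5.5 places the two-year follow-up after removal from study, and section 11.2 separates participation in the study from the 90 days after the last dose. Both weigh against the third reading, though neither is a definition.

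**The case against.** The strongest reply is that the conflict can do little harm in practice. Section 3.1 is an entry condition, and section 4.1 has an investigator confirm eligibility on a checklist. A vasectomised man must therefore have agreed to a barrier method or abstinence before 5.3.1 could apply to him. Section 6.1.4 repeats the rule for the study period and names sterilised men, whereas 5.3.1 is one general sentence under a heading about concomitant medication. Section 14.1 also reports accrual in the past tense, so a correction may reach few people.

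Most of this stands, and it keeps the point minor. It does not remove the conflict, because agreement at entry does not tell staff which section governs during treatment.

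A reader might go further and infer that 5.3.1 cancels the two-method rule or the 90-day period. The documents do not support that: both requirements remain in 3.1 and 6.1.4, and 5.3.1 merely omits them. A reader might also infer a demonstrated fetal hazard through sterilised men. The embryo-fetal toxicity described in the ixazomib toxicology section was seen in pregnant rabbits given the drug. The documents give no evidence of risk through a sterilised male partner.

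**Conclusion.** The point holds as a minor participant-safety inconsistency that should be corrected. The direct contradiction is confined to surgically sterilised men. The three looser points in 5.3.1 (the partner condition for men, no requirement of two methods for women, and the undefined period) call for alignment but are not contradictions of the same kind.

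The number of men affected is not given. Section 14.1 implies at most 27 − 1 = 26 treated participants of both sexes, which is a ceiling and not an estimate. There is no effect on sample size, power or analysis.

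The conclusion assumes that the odd verb in the 5.3.1 sentence means exempt; no other sensible reading removes the conflict. What the consent form tells participants cannot be seen here. The documents also do not say how many participants are still on treatment or within 90 days of their last dose, which is the group for whom a correction would matter most.

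**What to change.** Delete the contraception paragraph in 5.3.1, including the exemption sentence, and replace it with: *Contraception requirements are those stated in sections 3.1 and 6.1.4.* A bare cross-reference is better than restating the rules, because a third copy could drift again, and it settles the three looser points as well as the contradiction.

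The minimum alternative is to limit the exemption to surgically sterile female participants. That removes the contradiction but leaves the looser wording.

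Either way the cost is one short text change made as a routine amendment, with IRB approval before implementation under section 13.1. It adds no study procedure and does not touch sample size or analysis.

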5.3.2 Optional and Allowed Concomitant Medications

Supportive care is permitted as medically needed. Participants may receive supportive care with erythropoietin, darbepoetin, filgrastim or pegfilgrastim, in accordance with institutional guidelines.

Participants may receive RBC or platelet transfusions if clinically indicated in accordance with institutional guidelines. Participants who require repeated platelet transfusion support should be discussed with the principal investigator.

Participants may receive antiemetic and antidiarrheal medications as necessary, but these should not be administered unless indicated. Colony-stimulating factors may be used if neutropenia occurs but should not be given prophylactically.

All vitamins and supplements must be recorded from screening through the end of the participant's participation on trial.

Green tea and/or green tea supplements are prohibited while participating on trial.

5.4 Duration of Therapy

Duration of therapy will depend on individual response, evidence of disease progression and tolerance. In the absence of treatment delays due to adverse events, treatment may continue for 6 cycles of induction therapy with 6 cycles of maintenance or until one of the following criteria applies:

- Disease progression,
- Intercurrent illness that prevents further administration of treatment,
- Unacceptable adverse event(s),
- Participant demonstrates an inability or unwillingness to comply with the regimen and/or documentation requirements
- Participant decides to withdraw from the study, or
- General or specific changes in the participant's condition render the participant unacceptable for further treatment in the opinion of the treating investigator.

5.5 Duration of Follow Up

CONFIDENTIAL

This document is confidential. Do not disclose or use except as authorized.

Participants will be followed every six months (every 3 months preferred) for two years after removal from study until next therapy or until death. Participants removed from study for unacceptable adverse events will be followed until resolution or stabilization of the adverse event.

5.6 Criteria for Removal from Study

Participants will be removed from study when any of the criteria listed in Section 5.4 applies. The reason for study removal and the date the participant was removed must be documented in the study-specific case report form (CRF). Alternative care options will be discussed with the participant.

In the event of unusual or life-threatening complications, participating investigators must immediately notify the Principal Investigator, **[name], [contact].**

6. EXPECTED TOXICITIES AND DOSING DELAYS/DOSE MODIFICATIONS

Dose delays and modifications will be made using these recommendations. Toxicity assessments will be done using the CTEP Version 4 of the NCI Common Terminology Criteria for Adverse Events (CTCAE) Version 4.0, which is identified and located on the CTEP website at: http://ctep.cancer.gov/protocolDevelopment/electronic_applications/ctc.htm.

If possible, symptoms should be managed symptomatically. In the case of toxicity, appropriate medical treatment should be used (including antiemetic, antidiarrheal agents, etc.).

All adverse events experienced by participants will be collected from the time of the first dose of study treatment, through the study and until the final study visit. Participants continuing to experience toxicity at the off study visit may be contacted for additional assessments until the toxicity has resolved or is deemed irreversible.

6.1 Anticipated toxicities

6.1.1 Adverse Event Lists for Ixazomib

CONFIDENTIAL

This document is confidential. Do not disclose or use except as authorized.

Table 6-1 Most frequent treatment-emergent adverse events (in at least 10% of patients), overall safety population (part 1)

Primary System Organ Class Preferred Term	IV Total n = 146 n (%)	Oral Single		Oral Total n = 384 n (%)	Overall Total N = 530 n (%)
		Agent (3/4/7/9) n = 201 n (%)	Oral Combo (5/6/8/13) n = 173 n (%)		
Subjects with at Least One Adverse Event	145 (99)	197 (98)	163 (94)	370 (96)	515 (97)
Gastrointestinal disorders	115 (79)	160 (80)	139 (80)	306 (80)	421 (79)
Nausea	59 (40)	106 (53)	65 (38)	175 (46)	234 (44)
Diarrhoea	49 (34)	88 (44)	81 (47)	175 (46)	224 (42)
Vomiting	59 (40)	77 (38)	51 (29)	132 (34)	191 (36)
Constipation	36 (25)	46 (23)	57 (33)	105 (27)	141 (27)
Abdominal pain	27 (18)	33 (16)	14 (8)	49 (13)	76 (14)
General disorders and administration site conditions	118 (81)	151 (75)	132 (76)	288 (75)	406 (77)
Fatigue	88 (60)	103 (51)	76 (44)	181 (47)	269 (51)
Pyrexia	45 (31)	51 (25)	39 (23)	93 (24)	138 (26)
Oedema peripheral	30 (21)	27 (13)	61 (35)	89 (23)	119 (22)
Asthenia	10 (7)	31 (15)	20 (12)	51 (13)	61 (12)
Nervous system disorders	86 (59)	92 (46)	115 (66)	210 (55)	296 (56)
Headache	31 (21)	29 (14)	28 (16)	58 (15)	89 (17)
Dizziness	25 (17)	26 (13)	34 (20)	60 (16)	85 (16)
Neuropathy peripheral	16 (11)	21 (10)	45 (26)	66 (17)	82 (15)
Metabolism and nutrition disorders	88 (60)	107 (53)	91 (53)	204 (53)	292 (55)
Decreased appetite	55 (38)	64 (32)	25 (14)	92 (24)	147 (28)
Dehydration	25 (17)	37 (18)	12 (7)	49 (13)	74 (14)
Hypokalaemia	10 (7)	11 (5)	34 (20)	47 (12)	57 (11)
Blood and lymphatic system disorders	88 (60)	98 (49)	88 (51)	195 (51)	283 (53)
Thrombocytopenia	65 (45)	68 (34)	49 (28)	124 (32)	189 (36)
Anaemia	28 (19)	42 (21)	45 (26)	89 (23)	117 (22)

CONFIDENTIAL

This document is confidential. Do not disclose or use except as authorized.

Table 6-1 Most frequent treatment-emergent adverse events (in at least 10% of patients), overall safety population (part 2)

Primary System Organ Class Preferred Term	IV Total n = 146 n (%)	Oral Single		Oral Total n = 384 n (%)	Overall Total N = 530 n (%)
		Agent (3/4/7/9) n = 201 n (%)	Oral Combo (5/6/8/13) n = 173 n (%)		
Neutropenia	16 (11)	29 (14)	43 (25)	79 (21)	95 (18)
Lymphopenia	16 (11)	20 (10)	20 (12)	47 (12)	63 (12)
Skin and subcutaneous tissue disorders	83 (57)	90 (45)	102 (59)	195 (51)	278 (52)
Rash maculo-papular	21 (14)	13 (6)	29 (17)	44 (11)	65 (12)
Musculoskeletal and connective tissue disorders	78 (53)	93 (46)	99 (57)	193 (50)	271 (51)
Back pain	27 (18)	24 (12)	42 (24)	66 (17)	93 (18)
Pain in extremity	21 (14)	18 (9)	31 (18)	49 (13)	70 (13)
Arthralgia	17 (12)	28 (14)	22 (13)	50 (13)	67 (13)
Respiratory, thoracic and mediastinal disorders	87 (60)	78 (39)	80 (46)	161 (42)	248 (47)
Cough	31 (21)	28 (14)	36 (21)	64 (17)	95 (18)
Dyspnoea	30 (21)	30 (15)	26 (15)	56 (15)	86 (16)
Infections and infestations	48 (33)	89 (44)	92 (53)	184 (48)	232 (44)
Upper respiratory tract infection	12 (8)	31 (15)	35 (20)	66 (17)	78 (15)
Psychiatric disorders	32 (22)	35 (17)	73 (42)	113 (29)	145 (27)
Insomnia	14 (10)	12 (6)	50 (29)	67 (17)	81 (15)

Source: \biostatistics\MLNM9708\IB\2013\Tables\T14.1.3-TEAE_Pct10_Pooled

04APR2013 10:48

CONFIDENTIAL

This document is confidential. Do not disclose or use except as authorized.

Table 6-2 Treatment-emergent rash events, overall safety population (part 1)

MedDRA High-Level Term Preferred Term	Oral Single Agent		Oral Combo Agent	Oral Total n = 384 n (%)	Overall Total N = 530 n (%)
	IV (C16001/2) n = 146 n (%)	(C16003/4/7/9) n = 201 n (%)	(C16005/6/8/13) n = 173 n (%)		
Rashes, eruptions and exanthems NEC	41 (28)	40 (20)	54 (31)	96 (25)	137 (26)
Rash maculo-papular	21 (14)	13 (6)	29 (17)	44 (11)	65 (12)
Rash macular	15 (10)	23 (11)	22 (13)	45 (12)	60 (11)
Rash	10 (7)	8 (4)	12 (7)	20 (5)	30 (6)
Rash generalised	0	1 (< 1)	1 (< 1)	2 (< 1)	2 (< 1)
Rash vesicular	0	1 (< 1)	1 (< 1)	2 (< 1)	2 (< 1)
Rash morbilliform	0	1 (< 1)	0	1 (< 1)	1 (< 1)
Pruritus NEC	29 (20)	21 (10)	28 (16)	49 (13)	78 (15)
Rash pruritic	20 (14)	9 (4)	16 (9)	25 (7)	45 (8)
Pruritus	12 (8)	13 (6)	14 (8)	27 (7)	39 (7)
Pruritus generalised	0	0	1 (< 1)	1 (< 1)	1 (< 1)
Erythemas	15 (10)	9 (4)	15 (9)	24 (6)	39 (7)
Rash erythematous	12 (8)	3 (1)	8 (5)	11 (3)	23 (4)
Erythema	3 (2)	6 (3)	7 (4)	13 (3)	16 (3)
Palmar erythema	0	0	1 (< 1)	1 (< 1)	1 (< 1)
Papulosquamous conditions	13 (9)	8 (4)	7 (4)	15 (4)	28 (5)
Rash papular	13 (9)	8 (4)	7 (4)	15 (4)	28 (5)
Exfoliative conditions	4 (3)	8 (4)	4 (2)	12 (3)	16 (3)
Skin exfoliation	2 (1)	5 (2)	2 (1)	7 (2)	9 (2)
Exfoliative rash	2 (1)	2 (< 1)	0	2 (< 1)	4 (< 1)
Dermatitis exfoliative	0	1 (< 1)	2 (1)	3 (< 1)	3 (< 1)
Acute febrile neutrophilic dermatosis	0	2 (< 1)	1 (< 1)	3 (< 1)	3 (< 1)
Dermatitis allergic	0	0	3 (2)	3 (< 1)	3 (< 1)
Dermatitis acneiform	4 (3)	1 (< 1)	3 (2)	4 (1)	7 (1)
Erythema multiforme	0	2 (< 1)	1 (< 1)	3 (< 1)	3 (< 1)

CONFIDENTIAL

This document is confidential. Do not disclose or use except as authorized.

Table 6-2 Treatment-emergent rash events, overall safety population (part 2)

MedDRA High-Level Term Preferred Term	IV (C16001/2)	Oral Single Agent (C16003/4/7/9)	Oral Combo Agent (C16005/6/8/13)	Oral Total	Overall Total
	n = 146 n (%)	n = 201 n (%)	n = 173 n (%)	n = 384 n (%)	N = 530 n (%)
Stevens-Johnson syndrome	0	1 (< 1)	1 (< 1)	2 (< 1)	2 (< 1)
Interstitial granulomatous dermatitis	0	1 (< 1)	0	0	1 (< 1)
Vasculitic rash	0	1 (< 1)	0	1 (< 1)	1 (< 1)

Source: \\biostatistics\MLNM9708\IB\2013\Tables\T14.6.1-TEAE_AESI_Pooled;
\\biostatistics\MLNM9708\IB\2013\Tables\T14.1.2-TEAE_All 05APR2013 12:20.

6.1.2 Excluded Concomitant Medications and Procedures

The following medications and procedures are prohibited during the study:

- Systemic treatment with any of the following metabolizing enzyme inhibitors is not permitted during this study. **A drug-drug interaction [DDI] with a strong inhibitor would increase the ixazomib exposure and could lead to a higher probability of an AE).** Strong inhibitors of CYP1A2: fluvoxamine, enoxacin, ciprofloxacin.
- Strong inhibitors of CYP3A: clarithromycin, telithromycin, itraconazole, voriconazole, ketoconazole, nefazodone, and posaconazole. Systemic treatment with any of the following metabolizing enzyme inducers should be avoided unless there is no appropriate alternative medication for the patient’s use. **Unlike with inhibitors, if there were to be a DDI with an inducer, ixazomib exposure would be less; therefore, there would be a reduced chance of an AE. However, there may be less chance for an antitumor effect, but that is not an absolute reason to be taken off ixazomib.**
- Strong CYP3A inducers: rifampin, rifapentine, rifabutin, carbamazepine, phenytoin, and phenobarbital
- The dietary supplements St John’s wort and Ginkgo biloba are not permitted.

The following procedures are prohibited during the study:

- Any antineoplastic treatment with activity against WM (i.e. high-dose steroids, methotrexate, cyclophosphamide, etc.) except for drugs in this treatment regimen.
- Radiation therapy (**note that, in general, the requirement for local radiation therapy indicates disease progression**)
- **Platelet transfusions to help patients meet eligibility criteria are not allowed within 3 days prior to the blood draw that will confirm eligibility or any pre-dose CBC blood draws to guide dosing decisions (see Section 6.2.1.1)**

